8.7 Treatment Discontinuation Evaluations

End of study assessments will be done at 6 weeks (\pm 1 week) and at 16 weeks (\pm 1 week) of the last dose of study treatment, unless otherwise noted.

Participants with ongoing toxicities should be seen more often as clinically indicated. The schedule of clinical follow-up for these participants will be at the discretion of the treating physicians and according to established Standard of Care. AEs Assessment on the study, including assessment of immune-mediated AEs and SAEs, will continue for all participants until 90 days after the last study drug administration.

- 8.6.1 Review of medical history since last visit
- 8.6.2 Physical examination (vital signs, weight, performance status)
- 8.6.3 Review of changes in concurrent medications
- 8.6.4 Laboratory studies (as defined in Section 8.1.5)
 - a) CBC with differential and platelet count
 - b) Serum chemistries
 - c) Serum amylase and lipase
 - d) Serum or urine pregnancy test for WOCBP

- e) HIV viral load, performed using an assay with a limit of detection of 75 copies/ml or less, CD4/CD8, and repeat Hepatitis B antigen and/or Hepatitis C antibody if positive at baseline
- f) Immunologic labs consisting of rheumatoid factor, C-reactive protein, and ANA
- g) Endocrine labs consisting of: TSH, free T4, TPO, morning ACTH, and morning cortisol if ACTH is abnormal
- h) For participants with HIV-cHL and with bone marrow involvement at screening, a bone marrow biopsy will be required to confirm complete remission.
- 8.6.5 AE assessment
- 8.6.6 Biological sample submissions for correlative studies (as defined in Section 8.1.10), within 6 weeks (\pm 1 week) of the last dose of study treatment only
 - a) Collect two 6 ml red top tubes for assessment of circulating levels of proinflammatory molecules (Appendix XV).
 - b) The collection, shipping, and storage of 2x2 mm biopsies in RNALater and formalin is described in Appendix XIV (optional for KS cases only, with participant consent).
 - c) The collection, shipping, and storage of anal swabs is described in Appendix XVII (optional for anal cancer cases only, with participant consent).
 - d) Blood draw: Twelve 8.5mL ACD tubes for assays (HIV DNA, HIV RNA, SCA, and Pheno/ICS) for all participants who consent to this optional draw with hematocrit ≥ 25. *These tubes will be shipped directly to the* AMC Biorepository *for processing* (Appendix XVI).
 - e) If a participant has not consented to the HIV latent reservoir testing blood draw, two 8.5 yellow top tubes will be collected for herpesvirus load and latent virus studies (Appendix XIV).
- 8.6.7 Radiologic assessment of response, as applicable per Section 9.0.

For participants with KS, tumor, and response assessment with photographic documentation, as outlined in the KS Tumor Assessment MOP. Response of KS to treatment is described in Section 9.2. Scans will not be required for participants with KS unless clinically indicated.

In participants with HIV-cHL, F-FDG-PET/CT scans will be done at treatment completion. A combined FDG-PET/CT or FDG-PET + CT scan with and without IV contrast is required for this study. If a participant has an allergy to IV contrast, a non-IV contrast CT scan will be permitted. If the CT scan of a PET/CT hybrid is performed with both oral and IV contrast with contrast enhancement in the arterial and/or portal venous phase, with at least a 2-slice CT, and is acquired with at least 80 mAs and CT scans are obtained with contiguous sections (with a maximum of 5 mm slice thickness), then the PET/CT scan alone will suffice. If no contrast is

used in the FDG-PET/CT, an additional CT scan with contrast is required of the neck, chest, abdomen, and pelvis, see Section 8.1.7.

9.0 MEASUREMENT OF EFFECT

Although response is not the primary endpoint of this trial, participants with measurable disease will be assessed by standard criteria. For the purposes of this study, participants should be evaluated for response after cycle 4, and then re-evaluated every 12 weeks. In addition to a baseline scan, confirmatory scans will also be obtained 4 weeks following initial documentation of an objective response. Participants with KS will be evaluated for response before odd numbered cycles (5, 7, 9, etc.). Scans will not be required for participants with KS unless clinically indicated. Response of KS to treatment is described in Section 9.2. In participants with HIV-cHL, F-FDG-PET/CT scans will be done at cycles 9 and 13 (weeks 17 and 25). At cycle 24 (week 49), a F-FDG-PET/CT scan will be required for participants who do not have two consecutive negative scans before this time point. Refer to Section 9.3 for the 2017 RECIL Criteria for evaluating measurable disease in HIV-cHL.

9.1 Antitumor Effect – Solid Tumors

For the purposes of this study, participants should be evaluated for response after completing four cycles of therapy and re-evaluated for response every 12 weeks. In addition to a baseline scan, confirmatory scans should also be obtained 4 weeks following initial documentation of objective response.

Response and progression will be evaluated in this study using the new international criteria proposed by the revised RECIST guideline (version 1.1) [*Eur J Ca* 45:228-247, 2009]. Changes in the largest diameter (unidimensional measurement) of the tumor lesions and the shortest diameter in the case of malignant lymph nodes are used in the RECIST criteria.

For progression to visceral disease in participants with KS, see Section 9.2.4, Noncutaneous Progression.

9.1.1 Definitions

Evaluable for Toxicity: All participants will be evaluable for toxicity from the time of their first treatment with nivolumab and/or ipilimumab.

Evaluable for Objective Response: Only those participants who have measurable disease present at baseline, have received at least one cycle of therapy, and have had their disease re-evaluated will be considered evaluable for response. These participants will have their response classified according to the definitions stated below. (Note: Participants who exhibit objective disease progression prior to the end of cycle 1 will also be considered evaluable.)

Evaluable Non-Target Disease Response: Participants who have lesions present at baseline that are evaluable but do not meet the definitions of measurable disease, have received at least one cycle of therapy, and have had their disease re-evaluated will be considered evaluable for non-target disease. The response assessment is based on the presence, absence, or unequivocal progression of the lesions.

9.1.2 Disease Parameters

Measurable Disease: Measurable lesions are defined as those that can be accurately measured in at least one dimension (longest diameter to be recorded) as \geq 20 mm

by chest x-ray, as ≥ 10 mm with CT scan, or ≥ 10 mm with calipers by clinical exam. All tumor measurements must be recorded in millimeters (or decimal fractions of centimeters).

Note: Tumor lesions that are situated in a previously irradiated area might or might not be considered measurable. Such lesions should be considered measurable only if evidence of disease progression has been observed in this site. Disease present only in a previously irradiated field should have biopsy confirmation.

Malignant Lymph Nodes: To be considered pathologically enlarged and measurable, a lymph node must be ≥ 15 mm in short axis when assessed by CT scan (CT scan slice thickness recommended to be no greater than 5 mm). At baseline and in follow-up, only the short axis will be measured and followed.

Non-measurable Disease: All other lesions (or sites of disease), including small lesions (longest diameter <10 mm or pathological lymph nodes with ≥ 10 to <15 mm short axis), are considered non-measurable disease. Bone lesions, leptomeningeal disease, ascites, pleural/pericardial effusions, lymphangitis cutis/pulmonitis, inflammatory breast disease, and abdominal masses (not followed by CT or MRI), are considered as non-measurable.

Note: Cystic lesions that meet the criteria for radiographically defined simple cysts should not be considered as malignant lesions (neither measurable nor non-measurable) since they are, by definition, simple cysts.

'Cystic lesions' thought to represent cystic metastases can be considered as measurable lesions, if they meet the definition of measurability described above. However, if non-cystic lesions are present in the same participant, these are preferred for selection as target lesions.

Target Lesions: All measurable lesions up to a maximum of two lesions per organ and five lesions in total, representative of all involved organs, should be identified as target lesions and recorded and measured at baseline. Target lesions should be selected on the basis of their size (lesions with the longest diameter), be representative of all involved organs, but in addition should be those that lend themselves to reproducible repeated measurements. It may be the case that, on occasion, the largest lesion does not lend itself to reproducible measurement in which circumstance the next largest lesion which can be measured reproducibly should be selected. A sum of the diameters (longest for non-nodal lesions, short axis for nodal lesions) for all target lesions will be calculated and reported as the baseline sum diameters. If lymph nodes are to be included in the sum, then only the short axis is added into the sum. The baseline sum diameters will be used as reference to further characterize any objective tumor regression in the measurable dimension of the disease.

Non-target Lesions: All other lesions (or sites of disease) including any measurable lesions over and above the five target lesions should be identified as **non-target lesions** and should also be recorded at baseline. Measurements of these lesions are not required, but the presence, absence, or in rare cases unequivocal progression of each should be noted throughout follow-up.

9.1.3 Methods for Evaluation of Measurable Disease

All measurements should be taken and recorded in metric notation using a ruler or calipers. All baseline evaluations should be performed as closely as possible to the beginning of treatment and never more than 4 weeks before the beginning of the treatment.

The same method of assessment and the same technique should be used to characterize each identified and reported lesion at baseline and during follow-up. Imaging-based evaluation is preferred to evaluation by clinical examination unless the lesion(s) being followed cannot be imaged but are assessable by clinical exam.

Clinical Lesions: Clinical lesions will only be considered measurable when they are superficial (e.g., skin nodules and palpable lymph nodes) and ≥ 10 mm diameter as assessed using calipers (e.g., skin nodules). In the case of skin lesions, documentation by color photography, including a ruler to estimate the size of the lesion, is recommended.

Chest X-ray: Lesions on chest x-ray are acceptable as measurable lesions when they are clearly defined and surrounded by aerated lung. However, CT is preferable.

Conventional CT and MRI: This guideline has defined measurability of lesions on CT scan based on the assumption that CT slice thickness is 5 mm or less. If CT scans have slice thickness greater than 5 mm, the minimum size for a measurable lesion should be twice the slice thickness. MRI is also acceptable in certain situations (e.g. for body scans).

Use of MRI remains a complex issue. MRI has excellent contrast, spatial, and temporal resolution; however, there are many image acquisition variables involved in MRI, which greatly impact image quality, lesion conspicuity, and measurement. Furthermore, the availability of MRI is variable globally. As with CT, if an MRI is performed, the technical specifications of the scanning sequences used should be optimized for the evaluation of the type and site of disease. Furthermore, as with CT, the modality used at follow-up should be the same as was used at baseline and the lesions should be measured/assessed on the same pulse sequence. It is beyond the scope of the RECIST guidelines to prescribe specific MRI pulse sequence parameters for all scanners, body parts, and diseases. Ideally, the same type of scanner should be used, and the image acquisition protocol should be followed as closely as possible to prior scans. Body scans should be performed with breath-hold scanning techniques, if possible.

PET-CT: At present, the low dose or attenuation correction CT portion of a combined PET-CT is not always of optimal diagnostic CT quality for use with RECIST measurements. However, if the site can document that the CT performed as part of a PET-CT is of identical diagnostic quality to a diagnostic CT (with IV and oral contrast), then the CT portion of the PET-CT can be used for RECIST measurements and can be used interchangeably with conventional CT in accurately measuring cancer lesions over time. Note, however, that the PET portion of the CT introduces additional data, which may bias an investigator if it is not routinely or serially performed.

Ultrasound: Ultrasound is not useful in assessment of lesion size and should not be used as a method of measurement. Ultrasound examinations cannot be reproduced in their entirety for independent review at a later date and because they are operator dependent, it cannot be guaranteed that the same technique and measurements will be taken from one assessment to the next. If new lesions are identified by ultrasound in the course of the study, confirmation by CT or MRI is advised. If there is concern about radiation exposure at CT, MRI may be used instead of CT in selected instances.

Endoscopy, Laparoscopy: The utilization of these techniques for objective tumor evaluation is not advised. However, such techniques may be useful to confirm complete pathological response when biopsies are obtained or to determine relapse in trials where recurrence following CR or surgical resection is an endpoint.

Tumor Markers: Tumor markers alone cannot be used to assess response. If markers are initially above the upper normal limit, they must normalize for a participant to be considered in complete clinical response. Specific guidelines for both CA-125 response (in recurrent ovarian cancer) and PSA response (in recurrent prostate cancer) have been published [*JNCI* 96:487-488, 2004; *J Clin Oncol* 17, 3461-3467, 1999; *J Clin Oncol* 26:1148-1159, 2008]. In addition, the Gynecologic Cancer Intergroup has developed CA-125 progression criteria, which are to be integrated with objective tumor assessment for use in first-line trials in ovarian cancer [*JNCI* 92:1534-1535, 2000].

Cytology, Histology: These techniques can be used to differentiate between PR and CR in rare cases (e.g., residual lesions in tumor types, such as germ cell tumors, where known residual benign tumors can remain).

The cytological confirmation of the neoplastic origin of any effusion that appears or worsens during treatment when the measurable tumor has met criteria for response or SD is mandatory to differentiate between response or SD (an effusion may be a side effect of the treatment) and PD.

FDG-PET: While FDG-PET response assessments need additional study, it is sometimes reasonable to incorporate the use of FDG-PET scanning to complement CT scanning in assessment of progression (particularly possible 'new' disease). New lesions on the basis of FDG-PET imaging can be identified according to the following algorithm:

Negative FDG-PET at baseline, with a positive FDG-PET at follow-up is a sign of PD based on a new lesion. However, as this may not necessarily represent a new tumor lesion for individuals with ongoing HIV replication, new lesions on FDG-PET MUST be confirmed by CT scan to document PD.

No FDG-PET at baseline and a positive FDG-PET at follow-up: If the positive FDG-PET at follow-up corresponds to a new site of disease confirmed by CT, this is PD. If the positive FDG-PET at follow-up is not confirmed as a new site of disease on CT, additional follow-up CT scans are needed to determine if there is truly progression occurring at that site (if so, the date of PD will be the date of the initial abnormal FDG-PET scan). If the positive FDG-PET at follow-up

corresponds to a pre-existing site of disease on CT that is not progressing on the basis of the anatomic images, this is not PD.

FDG-PET may be used to upgrade a response to a CR in a manner similar to a biopsy in cases where a residual radiographic abnormality is thought to represent fibrosis or scarring. The use of FDG-PET in this circumstance should be prospectively described in the protocol and supported by disease-specific medical literature for the indication. However, it must be acknowledged that both approaches may lead to false positive CR due to limitations of FDG-PET and biopsy resolution/sensitivity.

Note: A 'positive' FDG-PET scan lesion means one which is FDG-avid with an uptake greater than twice that of the surrounding tissue on the attenuation corrected image.

9.1.4 Response Criteria

9.1.4.1 Evaluation of Target Lesions

Complete Response (CR): Disappearance of all target lesions. Any pathological lymph nodes (whether target or non-target) must have reduction in short axis to <10 mm.

Partial Response (PR): At least a 30% decrease in the sum of the diameters of target lesions, taking as reference the baseline sum diameters

Progressive Disease (PD): At least a 20% increase in the sum of the diameters of target lesions, taking as reference the smallest sum on study (this includes the baseline sum if that is the smallest on study). In addition to the relative increase of 20%, the sum must also demonstrate an absolute increase of at least 5 mm. (Note: the appearance of one or more new lesions is also considered progressions).

Stable Disease (SD): Neither sufficient shrinkage to qualify for PR nor sufficient increase to qualify for PD, taking as reference the smallest sum diameters while on study

9.1.4.2 Evaluation of Non-Target Lesions

Complete Response (CR): Disappearance of all non-target lesions and normalization of tumor marker level. All lymph nodes must be non-pathological in size (<10 mm short axis)

Note: If tumor markers are initially above the upper normal limit, they must normalize for a participant to be considered in complete clinical response.

Non-CR/Non-PD: Persistence of one or more non-target lesion(s) and/or maintenance of tumor marker level above the normal limits

Progressive Disease (PD): Appearance of one or more new lesions and/or *unequivocal progression* of existing non-target lesions. *Unequivocal progression* should not normally trump target lesion status. It must be representative of overall disease status change, not a single lesion increase.

Although a clear progression of "non-target" lesions only is exceptional, the opinion of the treating physician should prevail in such circumstances, and the progression status should be confirmed at a later time by the review panel (or Principal Investigator).

9.1.4.3 Evaluation of Best Overall Response

The best overall response is the best response recorded from the start of the treatment until disease progression/recurrence (taking as reference for progressive disease the smallest measurements recorded since the treatment started). The participant's best response assignment will depend on the achievement of both measurement and confirmation criteria.

Table 4: Response Evaluation for Participants with Measurable Disease (i.e., Target Disease)

Target Lesions	Non-Target Lesions	New Lesions	Overall Response	Best Overall Response when Confirmation is Required*
CR	CR	No	CR	≥4 wks. Confirmation**
CR	Non-CR/Non- PD	No	PR	≥4 wks. Confirmation**
CR	Not evaluated	No	PR	
PR	Non-CR/Non- PD/ Not evaluated	No	PR	
SD	Non-CR/Non- PD/ Not evaluated	No	SD	Documented at least once ≥4 wks. From baseline**
PD	Any	Yes or No	PD	No prior SD, PR or CR
Any	PD***	Yes or No	PD	
Any	Any	Yes	PD	

^{*} See RECIST 1.1 manuscript for further details on what is evidence of a new lesion.

Note: Participants with a global deterioration of health status requiring discontinuation of treatment without objective evidence of disease progression at that time should be reported as "*symptomatic deterioration*." Every effort should be made to document the objective progression even after discontinuation of treatment.

^{**} Only for non-randomized trials with response as primary endpoint.

^{***} In exceptional circumstances, unequivocal progression in non-target lesions may be accepted as disease progression.

Table 5: Response Evaluation for Participants with Non-Measurable Disease (i.e., Non-Target Disease)

Non-Target Lesions	New Lesions	Overall Response
CR	No	CR
Non-CR/non-PD	No	Non-CR/non-PD*
Not all evaluated	No	Not evaluated
Unequivocal PD	Yes or No	PD
Any	Yes	PD

^{* &#}x27;Non-CR/non-PD' is preferred over 'stable disease' for non-target disease since SD is increasingly used as an endpoint for assessment of efficacy in some trials so to assign this category when no lesions can be measured is not advised

9.1.5 Duration of Response

Duration of Overall Response: The duration of overall response is measured from the time measurement criteria are met for CR or PR (whichever is first recorded) until the first date that recurrent or PD is objectively documented (taking as reference for PD the smallest measurements recorded since the treatment started).

The duration of overall CR is measured from the time measurement criteria are first met for CR until the first date that PD is objectively documented.

Duration of Stable Disease: Stable disease is measured from the start of the treatment until the criteria for progression are met, taking as reference the smallest measurements recorded since the treatment started, including the baseline measurements.

9.2 Evaluation of Response for Participants with Kaposi Sarcoma

Response and progression will be evaluated for participants with KS using the ACTG response criteria for KS. For the purposes of this study, participants should be re-evaluated for response every 4 weeks. See Appendix I for the KS Tumor Assessment schedule. Refer to the AMC KS Tumor Assessment MOP for details regarding tumor assessment and photographic documentation.

Evaluable for Toxicity: All participants will be evaluable for toxicity from the time of their first dose of study drug.

Evaluable for Objective Response: Only those participants who have measurable disease present at baseline and have received study drug will be considered evaluable for response.

Response status will be classified as complete response (CR), partial response (PR), stable disease (SD), or progressive disease (PD).

- 9.2.1 Complete response (CR) is defined as the absence of any detectable residual disease, including tumor-associated edema, persisting for at least 4 weeks. Participants in whom pigmented (brown or tan) macular skin lesions persist after apparent complete response, biopsy of at least one representative lesion is required in order to document the absence of malignant cells. Participants without visceral disease are not required to undergo radiographic measurements. In participants known to have had visceral disease, an assessment at restaging with appropriate endoscopic or radiographic procedures should be made.
- 9.2.2 Partial response (PR) is defined as no new lesions (skin or oral), or new visceral sites of involvement (or the appearance or worsening of tumor-associated edema or effusions); AND
 - A 50% or greater decrease in the number of all previously existing lesions lasting for at least 4 weeks; OR
 - Complete flattening of at least 50% of all previously raised lesions (i.e., 50% of all previously nodular or plaque-like lesion become macules); OR
 - A 50% decrease in the sum of the products of the largest perpendicular diameters of the marker lesions

Note: Participants with residual tumor-associated edema or effusion who otherwise meet the criteria for complete response will be classified as having a partial response.

- 9.2.3 Stable disease (SD) is defined as any response not meeting the criteria for CR, PR, or PD.
- 9.2.4 Progressive disease (PD) is defined as follows:

For participants with ≤ 50 cutaneous lesions

- \geq 25% increase in the sum of perpendicular diameters of the indicator lesions, OR
- \geq 25% increase in the total lesion count, or a minimum of five new lesions, whichever is greater, OR
- ≥ 25% increase in the number of raised lesions (minimum of five new raised lesions if there are very few raised lesions, for example ≤ 8), whichever is greater.

Note: There are body sites where disease is particularly difficult to evaluate, and a few new lesions may be counted in spite of the fact that a participant is not actually progressing. For example, lesions of the foot, particularly those which are flat, are difficult to evaluate because their intensity may be variable based on how much edema is present, how much the person walked the day before, how long their feet have been in a dependent position prior to the physical exam, etc.

For participants with >50 cutaneous lesions

• 25% increase in the sum of the perpendicular diameters of the indicator lesions, OR

- 25% increase in the total number of lesions in the prospectively defined anatomic sites containing representative numbers of lesions, OR
- A total of five new lesions in anatomic sites which were previously documented as having no evidence of cutaneous disease on the whole-body diagram, OR
- 25% increase in the number of raised lesions (minimum of five raised lesions if there are very few raised lesions, for example <8) whichever is greater. Photographic documentation of "gross" or significant progression, particularly in areas that were not being followed, will be of particular value.

In order to classify a response as PR, the participant must have at least a PR in either the cutaneous or noncutaneous sites of disease, and no evidence of progression as defined in the above criteria. In order to classify a response as a CR, the participant must have a CR in both the cutaneous (if applicable) and noncutaneous (if applicable) sites of disease and no evidence of progression as defined by the above criteria.

Noncutaneous Progression

Progressive disease includes new visceral sites of involvement or progression of visceral disease or the development of new or increasing tumor-associated edema or effusion lasting at least 1 week, which interferes with the participant's normal activities. Progressive visceral disease, for measurable and evaluable disease, should be analogous to non-KS response criteria (RECIST; see Section 9.1).

- 9.2.5 Recurrent disease is defined as the appearance of tumor following documentation of a complete remission.
- 9.2.6 Time to response is defined as time from the first dose of chemotherapy until documentation of first response.
- 9.2.7 Time to progression is defined as time from initiation of chemotherapy to documentation of first progression.
- 9.2.8 Response duration is defined as the time from first documentation of response to documentation of first progression.

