3.1 Eligibility Criteria

3.1.1 Participants must have histologically confirmed solid tumor malignancy that is metastatic or unresectable and for which standard curative or palliative measures do not exist or are no longer effective. Participants with uncontrolled Kaposi sarcoma are permitted (KS must be increasing despite HAART and HIV suppression for greater than or equal to 2 months, or stable KS despite HAART for greater than or equal to 3 months).

For participants in the 24-participant solid tumor cohort, only those histologies not known to respond to single agent nivolumab (such as pancreas, prostate, and MSS colorectal cancer) will be excluded.

For participants in the relapsed refractory HIV-cHL expansion cohort, participants must have histologically confirmed, relapsed/refractory (defined as relapsed/refractory to one or greater lines of therapy) HIV-associated classical HL.

- 3.1.2 HIV-1 infection, as documented by any federally approved, licensed HIV rapid test performed in conjunction with screening (or ELISA, test kit, and confirmed by Western blot or other approved test). Alternatively, this documentation may include a record demonstrating that another physician has documented the participant's HIV status based on either: 1) approved diagnostic tests, or 2) the referring physician's written record that HIV infection was documented, with supporting information on the participant's relevant medical history and/or current management of HIV infection.
- 3.1.3 Participants must have measurable disease, defined as at least one lesion that can be accurately measured in at least one dimension (longest diameter to be recorded for non-nodal lesions and short axis for nodal lesions) as ≥20 mm with conventional techniques or as ≥10 mm with spiral CT scan, MRI, or calipers by clinical exam. Scans must have been performed within 4 weeks prior to registration. See Section 9.1.3 or Section 9.3 for HL for the evaluation of measurable disease. Note: For participants with Kaposi sarcoma, the following apply: At least five measurable cutaneous KS lesions or any number of lesions with systemic unresectable disease

with no previous local radiation, surgical, or intralesional cytotoxic therapy that would prevent response assessment.

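### Kaposi sarcoma partial response by flattening or by lesion area needs no 4-week persistence, so with one or two raised lesions a single reading can count as a response

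*Combined protocol and SAP*

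**What the plan says.** Section 9.2.1 defines a KS complete response as "absence of any detectable residual disease, including tumor-associated edema, persisting for at least 4 weeks". Section 9.2.2 then lists three cutaneous routes to PR, joined by OR:

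- count: "A 50% or greater decrease in the number of all previously existing lesions lasting for at least 4 weeks; OR"
- flattening: "Complete flattening of at least 50% of all previously raised lesions"
- area: "A 50% decrease in the sum of the products of the largest perpendicular diameters of the marker lesions"

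The 4 weeks stand inside the first item, before its semicolon. All three routes also require no new lesions, no new visceral site and no new or worse edema or effusion. Section 9.2.4 adds that there must be no progression.

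Eligibility criterion 3.1.3 asks KS participants for "At least five measurable cutaneous KS lesions or any number of lesions with systemic unresectable disease". It does not mention raised lesions. The progression rule in 9.2.4 does guard against small numbers, with a "minimum of five new raised lesions if there are very few raised lesions".

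On timing, Section 9.2 says "participants should be re-evaluated for response every 4 weeks". Section 10.4.1 counts KS responses in the objective response rate (ORR), reports disease-specific rates for histologies with more than five participants, and summarizes duration of response.

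**The concern.** Complete response and the count route are protected from a one-off reading by the 4-week requirement; the other two routes are not. The flattening route is the more exposed, because it is a proportion of a number that may be very small. With one or two raised lesions, one lesion read as flat already meets the 50% threshold.

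A false PR of this kind is not reversed. If the lesion is read as raised again 4 weeks later, one lesion falls short of the five-lesion floor for progression. Recurrence in 9.2.5 applies only after a complete remission. Response duration in 9.2.8 simply runs from first documentation to first progression. Entry under 3.1.1 includes KS that is stable despite HAART, so a participant with no treatment effect can satisfy the no-progression condition for many visits.

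At stake is the KS part of secondary objective 1.2.2. At the smallest reportable number, six KS participants, one false PR moves the KS ORR by 1/6 = 17 percentage points. It also enters the duration-of-response summary.

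**Working it through.** **Does another section supply confirmation?**

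| Place | What it offers | Reaches a KS PR? |
|---|---|---|
| 9.1.4.3, Table 4 | 4-week confirmation, footnoted to trials with response as primary endpoint | No; 9.0 says response is not primary here |
| 9.0 and 9.1 | Confirmatory scan 4 weeks after first response | Not routinely; KS is scanned only if clinically indicated |
| Appendix XII | Photographs when the response category changes | Documents the change; does not require it to last |
| ACTG criteria and KS Tumor Assessment MOP, cited in 9.2 | Not in the documents | Cannot be checked |

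**The plan's own figures.** The only response-rate figures are the exact intervals in 10.2. They reproduce with non-integer responder counts: 0.70 × 12 = 8.4 gives 38.0% to 92.0%, and 0.70 × 24 = 16.8 gives 48.1% to 86.8%. They describe sampling precision and say nothing about misclassification.

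**Number of looks.** For 46-cycle cohorts, Sections 8.4.6 and 8.5.7 put KS assessments before cycles 3, 5, 7, …, 45, up to 22 on treatment. Six are done by cycle 13 (week 24). The combination expansion schedule in Appendix I gives cycle 3, odd cycles 5 to 13 and cycles 14 to 22: 1 + 5 + 9 = about 15.

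**Chance of a false PR by flattening.** Let k be the number of raised lesions, and q the chance that an unchanged raised lesion is read as flat at a visit. The value of q is an assumption (range 2% to 10%).

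- Lesions needed: m = k/2 rounded up, so 1 for k = 1 or 2, 2 for k = 3 or 4, and 3 for k = 5 or 6.
- Per visit: p = P(Binomial(k, q) ≥ m).
- At any of V visits, errors independent: 1 − (1 − p)^V.
- At two consecutive visits: a recursion. Let a be the chance of no PR yet and no hit at the last visit, b the chance of no PR yet but a hit there, and d the chance of a confirmed PR. Each visit updates a to (a + b)(1 − p), b to a·p, and d to d + b·p.

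Example: k = 2, q = 5%. Then p = 1 − 0.95² = 9.75%. Over 6 visits, 1 − 0.9025⁶ = 1 − 0.95¹² = 46.0%. The recursion gives 4.4%.

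False-PR chance over 6 visits, any single visit → two consecutive visits:

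| k | q = 2% | q = 5% | q = 10% |
|---|---|---|---|
| 1 | 11.4% → 0.2% | 26.5% → 1.2% | 46.9% → 4.6% |
| 2 | 21.5% → 0.8% | 46.0% → 4.4% | 71.8% → 15.0% |
| 4 | 1.4% → <0.1% | 8.1% → 0.1% | 27.6% → 1.3% |
| 5 | <0.1% → <0.1% | 0.7% → <0.1% | 5.0% → <0.1% |
| 10 | <0.1% → <0.1% | <0.1% → <0.1% | 1.0% → <0.1% |

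**If errors carry over.** Suppose each lesion keeps its previous reading state with probability 0.3 or 0.6 and is otherwise redrawn (simulation, 100,000 participants, k = 2, q = 5%, 6 visits). The change is then 37% → 12% and 26% → 15%.

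**Area route.** Assume lognormal error on each diameter with a coefficient of variation of 10% to 20%. With five marker lesions the false-PR chance is at most 0.1%, even over 23 assessments. With one marker lesion and 15% to 20% error it is 12% to 31% over 23, but Appendix XII asks for five marker lesions in all participants.

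**The case against.** Five objections carry weight.

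1. **Unseen sources.** The ACTG criteria or the KS MOP may contain a persistence rule. This stands as a reason to check them before amending. It does not excuse 9.2.2, which writes the duration into one route and omits it from two.
2. **Unconfirmed response as a trial-wide choice.** Given the Table 4 footnote, other solid tumors in the pooled ORR may also count unconfirmed PRs. This stands as a comparability point and is answered by reporting both definitions. Within KS the rule is already mixed.
3. **The error rate is invented.** True; the percentages show how the rule behaves, not what will happen. Flattening must be complete, and photographs allow a reading to be checked. No document says how many participants will have only one or two raised lesions.
4. **The other PR conditions are not modelled.** A miscounted new lesion blocks a PR, so these conditions lower the figures. A reader might infer that the KS ORR is certainly biased upward. The documents support only that this route can inflate it; the net effect of all reading errors is unknown.
5. **The number of looks.** A reader might apply 22 on-treatment looks, or 23 with the off-study visit, to every KS participant. The combination expansion cohort has about 15, and a participant with no effect may leave early on progression.

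A further temptation is to borrow the five in 9.2.4 as a baseline minimum of raised lesions. That figure counts new raised lesions for progression, so the documents do not support using it that way.

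**Conclusion.** The gap is in the text: two of the three KS PR routes need no persistence, and nothing else in the documents adds it. The practical risk lies mainly in the flattening route with one or two raised lesions. With three or four, two lesions must be misread together. From about five raised lesions it is small when the error is 5% or less, and the area route is negligible with five marker lesions.

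The size rests on the assumed error rate, on how far errors repeat between visits, and on leaving out the no-new-lesion and no-progression conditions. Persistence helps in every case examined, but much less when the same misreading tends to recur. The matter concerns a secondary, preliminary endpoint; no DLT or MTD decision depends on it. It is worth correcting because the correction is cheap.

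**What to change.** After checking the ACTG criteria and the KS MOP for consistency, state at the head of 9.2.2 that all three PR alternatives must last at least 4 weeks, meaning present at two consecutive scheduled KS assessments, with the response dated at the first of the two. Report the ORR under the present, unconfirmed definition as a sensitivity analysis; this preserves comparability with participants already assessed and with the RECIST-assessed tumors.

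Do not add a baseline minimum of raised lesions. Instead, for each PR that rests on flattening alone, report the number of raised lesions at baseline, so that readers can see which responses depend on one lesion.

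The cost is a short amendment and one extra tabulation. Assessments are already 4-weekly, so no visit is added. The downside is that a real PR first seen at the last assessment is not counted, so the KS ORR may be slightly lower.
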